### **Type of Research**

This study was planned as a randomized study in a pre-test post-test design.

### **Location and Features of the Research**

The research is scheduled for April 2019 - August 2019. The hospital consists of a total of 3 buildings with the main building with 10-storey clinics, the oncology building and the heart structure. The hospital has 1010 beds of beds. The research was conducted in outpatient clinics, operating rooms, pediatrics and emergency inpatient services. Information about the inpatient services of the study is given in (Annex-4). A total of 745 employees are employed at the hospital. Number of employees in the services included in the study.

#### Research Criteria

-The nurses working in the inpatient services of the hospital where the research was conducted were included in the research.

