#### Exclusion criteria from the study

Nurses who did not agree to participate in the study and who wanted to quit while the research was continuing were excluded.

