#### Nurse introduction form (Annex-5)

Six of the nurses' socio-demographic characteristics (gender, age, educational status, total working time in the profession, service and status), injection practice (frequency of intramuscular injection, participation in the in-service training program for intramuscular

injections and participated in in-service training) consists of a total of nine questions, three of which are about time.

Observation form of the procedure steps of intramuscular injection with the Z technique from the ventrogluteal region (Annex-6)

It is a 20-item form consisting of intramuscular injection application steps from the ventroluteal region with the Z technique. This form is in line with the literature (Yapucu Güneş, Zaybak, Biçici, & Çevik, 2009; Gülseven-Karabacak, 2010; Kaya & Palloş, 2014; Gülnar & Özveren, 2016; Dikmen & Akın-Korhan, 2016; Şanlıalp-Zeyrek & Kuzu-Kurban, 2017; Göçmen-Baykara, Çalışkan, Öztürk and Karadağ, 2019) were prepared by researchers. Opinions of four experts were taken for the validity and reliability of the questions in the form ([name], [name], [name], [name]). In line with the suggestions, the observation form was given its final form.

Student satisfaction and self-confidence in learning scale (ÖMÖKGÖ) (Annex-7)

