## Data Collection

The nurses in the services of Health, Practice and Research Hospital included in the research were reached and informed about the research. Nurses who met the sampling criteria of the study and agreed to participate in the study were informed verbally and in writing by the researcher.

The nurses were randomized according to their educational status and divided into groups. For each training, the place, day and time of the training were announced to the nurses who accepted the research, and the nurses who would come to the training were determined in advance as the experimental and control groups. Groups of minimum 3 and maximum 12 nurses were invited to each training. The trainings continued until the number determined for the experimental and control groups was reached. All trainings were conducted by the same researcher in order to minimize personal error in trainings. Since the single-blind method was used while collecting the data, the nurses in the experimental and control groups did not know which group they belonged to. In the pre-test, the trainings were carried out in two stages, Training I and Training II. A post-test was carried out after at least two and at most four weeks (Gülnar & Özveren, 2016; Eroğlu & Çevik, 2019).

Training I: Nurses in the experimental and control groups were interviewed in advance on the day and time they were available. Nurses who were available on the same day and time were grouped into small groups of 3-12 people. Theoretical training was given to the nurses in both groups, with a 10-minute power-point presentation prepared in line with the literature on intramuscular injection, in the training hall of Health, Practice and Research Hospital, which was predetermined and permission was obtained by the researcher. The content of the presentation includes information about evidence-based applications such as intramuscular injection from the VG region, determining the VG region, Z technique, and airlock technique (Annex-8).

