### Evaluation of Data

The data obtained in the research were analyzed using the SPSS (Statistical Package for Social Sciences) for Windows 25.0 program. For the information collected from the experimental and control groups, the frequency, percentage values, mean and standard deviation, which are descriptive statistics, were interpreted. Chi-square analysis was used to measure whether the introductory features showed similar distribution in the experimental and control groups. Q-Q Plot plot was used to determine the conformity to the normal distribution (Chan, 2003:280-285). In addition, the normal distribution of the data used depends on the skewness and kurtosis values being between  $\pm 3$  (Shao, 2002). In this study, it was observed that the Student Satisfaction and Self Confidence in Learning scales had a normal distribution.

Independent sample t-test was used to test whether the scores obtained from two unrelated samples differed significantly from each other, and the McNemar test was used for the variation of two dependent groups in different time periods. The reliability coefficient of the scale of student satisfaction and self-confidence in learning was calculated as 0.914. In cases where the error rate was  $p < 0.05$  in all tests, the difference between the groups was considered statistically significant. Comments were made in the light of the tables created by the analysis of the data.

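### Prior injection training and injection frequency are recorded but left out of the arm comparison; a baseline chi-square is no substitute for covariate adjustment

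*Combined protocol and SAP*

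**What the plan says.** Research Criteria sets one entry condition: "The nurses working in the inpatient services of the hospital where the research was conducted were included in the research". The exclusion section removes only refusers and those who withdraw: "Nurses who did not agree to participate in the study and who wanted to quit while the research was continuing were excluded". Neither mentions earlier injection training.

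The nurse introduction form (Annex 5) has nine questions. Three concern injection practice: how often the nurse injects, whether the nurse has had earlier training ("participation in the in-service training program for intramuscular"), and when that training took place.

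Data Collection names one factor in the allocation: "The nurses were randomized according to their educational status and divided into groups".

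Evaluation of Data gives the Annex 5 items one inferential use: "Chi-square analysis was used to measure whether the introductory features showed similar distribution in the experimental and control groups". For outcomes it names two tests, neither with covariates. One compares separate samples: "Independent sample t-test was used to test whether the scores obtained from two unrelated samples differed significantly from each other". The other, McNemar's test, is for change over time in paired data.

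The research type is a pre-test post-test design. The procedure for the experimental group has each nurse observed on the simulator with the 20-item form before any teaching. Evaluation of Data does not use that pre-test result as a covariate.

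**The concern.** The trial asks whether simulator practice adds to a slide presentation. Earlier training in intramuscular injection, and how often a nurse injects, plausibly predict both technique and self-confidence. The plan collects these items and then does two unhelpful things with them.

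First, it tests them for baseline similarity. If the lottery was sound, any difference arose by chance, so the test answers no useful question. At about 48 per arm it also overlooks sizeable differences, and whatever its result it corrects nothing.

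Second, it leaves them out of the comparison. Outcome variation that they could explain stays in the error term, and a chance imbalance passes straight into the estimated difference.

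**Working it through.** The documents give no figure on this point to reproduce. Neither the share of nurses with prior training nor its effect on the score is stated.

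**Inputs.** Arm sizes of 47 and 48 come from Population and Sample of the Research. *Assumed:* share previously trained p = 20%, 35% or 50%; effect of prior training b = 0.5 SD, with 1.0 SD as a high case. SD here means the residual SD among nurses of equal training status.

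**Step 1: chance imbalance.** SD of the difference in shares = √[p(1−p)(1/47 + 1/48)]. The probabilities are exact binomial.

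| p | SD of difference | P(≥10 points) | P(≥15 points) | P(≥20 points) |
|---|---|---|---|---|
| 20% | 8.2 points | 24% | 7% | 1.5% |
| 35% | 9.8 points | 28% | 13% | 4.1% |
| 50% | 10.3 points | 30% | 15% | 5.1% |

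**Step 2: shift in the unadjusted difference.** Shift = b × imbalance. Standard error of the arm difference = √(1/47 + 1/48) = 0.205 SD. With b = 0.5:

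| p | Typical shift (1 SD of imbalance) | 95% bound (1.96 SD) |
|---|---|---|
| 20% | 0.5 × 0.082 = 0.041 SD | 0.080 SD |
| 35% | 0.5 × 0.098 = 0.049 SD | 0.096 SD |
| 50% | 0.5 × 0.103 = 0.051 SD | 0.101 SD |

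The typical shift is 20% to 25% of the standard error, and the bound 39% to 49%.

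**Step 3: what the baseline chi-square can detect.** It reaches p < 0.05 roughly when the observed difference exceeds 1.96 × SD, that is 16 points (p = 20%) to 20 points (p = 50%). Put as power, it detects a true 15-point difference 31% to 45% of the time and a true 10-point difference 16% to 23%. A non-significant result is weak evidence of balance.

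**Step 4: effect on the test.** Scores were simulated as normal error plus b × prior training plus an arm effect, with 6,000 runs per setting. The t-test was compared with a linear model that adjusts for prior training.

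- No arm effect: rejection was 4.7% to 5.3%, adjusted or not.
- No arm effect, restricted to runs where the experimental arm had at least 15 points more trained nurses: the unadjusted test rejected in about 5% to 10% (b = 0.5) or 11% to 13% (b = 1.0). These rest on 248 to 470 runs each and are rough.
- Arm effect of 0.58 SD: adjustment raised power as follows.

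| p | b = 0.5: unadjusted → adjusted | b = 1.0: unadjusted → adjusted |
|---|---|---|
| 20% | 78.8% → 80.0% | 74.4% → 80.3% |
| 35% | 77.6% → 79.7% | 72.0% → 79.2% |
| 50% | 77.1% → 79.3% | 70.6% → 79.1% |

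**The case against.** The main objection is that randomisation already deals with this. Chance imbalance in any covariate is part of what the test's error rate allows for, and Step 4 confirms it. That stands. A reader might infer that the comparison is biased or that false positives are inflated; the documents do not support either. The higher rejection rates in Step 4 apply only to the minority of allocations with a large imbalance in one direction.

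A reader might also infer that admitting trained nurses without a washout is a design error. It is not: both arms draw on the same open population, and Limitations of the Research confines generalisation to that study group. Nor do the documents say that nurses who rarely inject took part, or that untrained nurses are the main target. An analysis limited to untrained nurses is therefore optional.

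Four further objections hold in part:

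- The pre-test observation measures starting skill more directly than training history does. Adjustment for the observation-form outcome should include it.
- Evaluation of Data does not clearly name a between-arm test for the observation form, so the point is firmest for scores compared by t-test.
- A yes/no training item treats recent and distant training alike. That limits the gain but does not distort the comparison.
- The sample section is badly garbled and also speaks of making the groups similar on preliminary characteristics. Data Collection, which is clearer, names education alone.

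**Conclusion.** The point holds as a minor weakness of the analysis. Relevant baseline items already in hand are used for description and a low-power similarity test, while the arm comparison is unadjusted. Eligibility needs no change, and the type I error is near 5% either way.

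With 20% to 50% previously trained and a 0.5 SD effect, the conditional shift is typically 0.04 to 0.05 SD and at most about 0.10 SD at the 95% bound; the power forgone is about 1 to 2 percentage points. At a 1.0 SD effect the power forgone would be about 6 to 8 points. Both inputs are assumptions. If prior training hardly affects the scores, there is almost nothing to gain.

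**What to change.** In Evaluation of Data, replace the unadjusted between-arm t-test with a linear model (ANCOVA) containing arm, education stratum, prior in-service intramuscular-injection training and injection frequency. Fix these covariates without regard to the chi-square results. For the observation-form outcome, add the pre-test score and state how the form is summarised for the between-arm comparison. Report the Annex 5 comparison descriptively, with no significance test.

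The cost is a few degrees of freedom out of 95 nurses and slightly more analysis, with no new data. If the observation form is analysed step by step, the work is greater: up to 20 binary models in place of one linear model on a total. The document already reports results from this study, such as the scale's reliability of 0.914, so the analysis may be complete. In that case label the adjusted model post hoc and show it beside the unadjusted result.

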#### Exclusion criteria from the study

Nurses who did not agree to participate in the study and who wanted to quit while the research was continuing were excluded.

#### Research termination criteria

The study was terminated when the required sample size was reached.

#### Data Collection Tools

The data of the study were collected using the nurse identification form (Annex 5), the Ventrogluteal Region Z Technique and the Intramuscular Injection Application Procedure Steps Observation Form (Appendix-6) and the Student Satisfaction and Self-Confidence in Learning Scale (Annex-7).

#### Nurse introduction form (Annex-5)

Six of the nurses' socio-demographic characteristics (gender, age, educational status, total working time in the profession, service and status), injection practice (frequency of intramuscular injection, participation in the in-service training program for intramuscular

injections and participated in in-service training) consists of a total of nine questions, three of which are about time.

Observation form of the procedure steps of intramuscular injection with the Z technique from the ventrogluteal region (Annex-6)

It is a 20-item form consisting of intramuscular injection application steps from the ventroluteal region with the Z technique. This form is in line with the literature (Yapucu Güneş, Zaybak, Biçici, & Çevik, 2009; Gülseven-Karabacak, 2010; Kaya & Palloş, 2014; Gülnar & Özveren, 2016; Dikmen & Akın-Korhan, 2016; Şanlıalp-Zeyrek & Kuzu-Kurban, 2017; Göçmen-Baykara, Çalışkan, Öztürk and Karadağ, 2019) were prepared by researchers. Opinions of four experts were taken for the validity and reliability of the questions in the form ([name], [name], [name], [name]). In line with the suggestions, the observation form was given its final form.

Student satisfaction and self-confidence in learning scale (ÖMÖKGÖ) (Annex-7)

The Turkish validity and reliability study was conducted by Karaçay and Kaya (2017) and it consists of two sub-dimensions as "Satisfaction in Learning" and "Self-Confidence in Learning" and a total of 13 items (Karaçay and Kaya, 2017). There are five sub-items in the satisfaction in learning sub-dimension and eight sub-items in the self-confidence in learning sub-dimension. The 13th item in the scale was revised by the researchers (Karaçay, P. Kaya, H. 2017). The answer options are 1=Strongly Disagree, 2=Disagree, 3=Neither Agree or Disagree, 4=Agree, 5=Strongly Agree. The score obtained is obtained from the sum of the items of the scale. The highest total score that can be obtained from the scale is 65 and the lowest is 13. The Cronbach Alpha value of the scale is 0.85 for "Satisfaction in Learning", 0.77 for "Self-Confidence in Learning", and 0.89 for the total scale. The sum of the sub-dimensions of the scale does not give the total score. Scale scores; It is obtained by dividing the sum of the sub-dimensions by the number of items. The high score that can be obtained from the total of the scale indicates high satisfaction and self-confidence (Ünver et al., 2017). In this study, the internal consistency coefficient of the scale was 0.914, the internal consistency coefficient of student satisfaction was 0.826, and the internal consistency coefficient of the self-confidence in learning sub-dimension was 0.880. Since the reliability coefficients of the Student Satisfaction and Self-Confidence in Learning Scale (SMCDS) and its sub-dimensions vary between 0.826 and 0.914, the scale was found to be reliable.

## Data Collection

The nurses in the services of Health, Practice and Research Hospital included in the research were reached and informed about the research. Nurses who met the sampling criteria of the study and agreed to participate in the study were informed verbally and in writing by the researcher.

The nurses were randomized according to their educational status and divided into groups. For each training, the place, day and time of the training were announced to the nurses who accepted the research, and the nurses who would come to the training were determined in advance as the experimental and control groups. Groups of minimum 3 and maximum 12 nurses were invited to each training. The trainings continued until the number determined for the experimental and control groups was reached. All trainings were conducted by the same researcher in order to minimize personal error in trainings. Since the single-blind method was used while collecting the data, the nurses in the experimental and control groups did not know which group they belonged to. In the pre-test, the trainings were carried out in two stages, Training I and Training II. A post-test was carried out after at least two and at most four weeks (Gülnar & Özveren, 2016; Eroğlu & Çevik, 2019).

Training I: Nurses in the experimental and control groups were interviewed in advance on the day and time they were available. Nurses who were available on the same day and time were grouped into small groups of 3-12 people. Theoretical training was given to the nurses in both groups, with a 10-minute power-point presentation prepared in line with the literature on intramuscular injection, in the training hall of Health, Practice and Research Hospital, which was predetermined and permission was obtained by the researcher. The content of the presentation includes information about evidence-based applications such as intramuscular injection from the VG region, determining the VG region, Z technique, and airlock technique (Annex-8).

Training II: The experimental group was given skill training on applying intramuscular injection with the Z technique from the VG region on the simulator, in line with the intramuscular injection application steps, by using a low-fidelity intramuscular injection simulator immediately after the theoretical training with a powerpoint presentation. Afterwards, all nurses were asked to make intramuscular injections on the simulator, accompanied by the researcher. In order for this practice to be fully understood and turned

into a skill, the nurses in the experimental group were allowed to repeat the practice under the supervision of the researcher until they did all the steps correctly.

In order to facilitate the participation of nurses, the trainings were held in the training hall of the hospital, with verbal permission from the Chief Physician of Health, Practice and Research Hospital. For the use of the low-fidelity intramuscular injection simulator used in the trainings, Faculty of Health Sciences Nursing Department Head was contacted and verbal permission was obtained. The training room for the presentation and the materials required for the intramuscular injection application (simulator, gloves, injector, needle tip, medicine, cotton, alcohol, kidney tub, piercing-cutting waste box) were prepared by the researchers before the training.

#### Pre-application

Before the implementation phase of the study, a preliminary application was carried out with 10 nurses working in the adult inpatient clinics of Health, Application and Research Hospital and Kütahya Yoncalı Physical Therapy and Rehabilitation Hospital. These nurses were not included in the research sample. Since it was seen that the items were understandable after the pre-application, no changes were made in the items.

#### Study procedure for the experimental group

After the nurses who attended the training were informed about the research, they were asked to read and sign the informed consent form. Afterwards, the nurses answered the questions in the questionnaire. Then, each nurse was asked to make an intramuscular injection from the VG region using the Z technique on a low-fidelity intramuscular injection simulator. Meanwhile, the nurses were observed by the researcher according to the "Intramuscular Injection Application Procedure Steps Observation Form with the Ventrogluteal Region Z Technique" (Annex 6), and this form was filled by the researcher (Pre-test). After all the nurses who came to the training that day were observed one by one, a 10-minute powerpoint presentation was given by the researcher to all the nurses who came to the training at the same time regarding the steps of applying intramuscular injection from the VG region with the Z technique (Training I) (Annex-8). Immediately afterwards, an injection application was made on the simulator by the researcher with the demonstration method according to the "Procedure Steps of Intramuscular Injection with the Z Technique from the Ventrogluteal Region". This process was first ensured by the nurses, and then each nurse who came to the training that day was provided to inject on the simulator one by one in accordance with the "Intramuscular

"Injection Procedure Steps with the Z Technique from the Ventrogluteal Region" (Training II). Until each nurse does all the steps correctly under the supervision of the researcher.

### Evaluation of Data

The data obtained in the research were analyzed using the SPSS (Statistical Package for Social Sciences) for Windows 25.0 program. For the information collected from the experimental and control groups, the frequency, percentage values, mean and standard deviation, which are descriptive statistics, were interpreted. Chi-square analysis was used to measure whether the introductory features showed similar distribution in the experimental and control groups. Q-Q Plot plot was used to determine the conformity to the normal distribution (Chan, 2003:280-285). In addition, the normal distribution of the data used depends on the skewness and kurtosis values being between  $\pm 3$  (Shao, 2002). In this study, it was observed that the Student Satisfaction and Self Confidence in Learning scales had a normal distribution.

Independent sample t-test was used to test whether the scores obtained from two unrelated samples differed significantly from each other, and the McNemar test was used for the variation of two dependent groups in different time periods. The reliability coefficient of the scale of student satisfaction and self-confidence in learning was calculated as 0.914. In cases where the error rate was  $p < 0.05$  in all tests, the difference between the groups was considered statistically significant. Comments were made in the light of the tables created by the analysis of the data.

